- HYPOTHESES:**
- i. The fitting success rate for a combination of two senofilcon A designs is greater than for a single design when fitted to a population skewed to larger corneas.
 - ii. The fitting success rates for senofilcon A designs are equivalent to those predicted by the Young model.
 - iii. The fitting characteristics (tightness, corneal overlap) for senofilcon A designs are equivalent to those predicted by the Young model.
- TEST PRODUCTS:** Both lens types are manufactured by JJVC, in senofilcon A material with 38% water content and a shrinkage factor (20→34°C) of 0.997. Both are available in powers -1.00 to -6.00D and are CE marked.
- Acuvue® 1-Day Oasys with HydraLuxe™ (8.50/14.3)
 - Acuvue® OASYS® with HydraClear Plus™ (8.40/14.0, 8.80/14.0)
- LENS CARE PRODUCTS:** Unpreserved saline for rinsing, e.g. Saufion saline.
- NO. SUBJECTS:** Approximately 40-60 subjects. An attempt will be made to include ~50% subjects who have an HVID >11.75mm or corneal diameter >13.75mm.
- STUDY POPULATION:** Volunteer subjects will be enrolled if they meet the baseline screening criteria and the inclusion and exclusion listed below. Ideally at least half of the eyes will fall within the top quartile of average corneal diameters ie >HVID 11.75mm or corneal diameter >13.75mm or will have demonstrated loose / tight fitting contact lenses in previous studies.

Inclusion Criteria:

- i. Age 18-70 years.
- ii. Able to read, comprehend and sign an informed consent.
- iii. Willing to comply with the wear and study assessment schedule.
- iv. Spherical distance prescription between -0.50 and -6.00 (inc.).
- v. Astigmatism, if present, ≤ 1.50 DC in both eyes.
- vi. Have normal eyes with no evidence of any ocular abnormality or disease. For the purposes of this study a normal eye is defined as one having:
 - A clear central cornea
 - No anterior segment disorders
 - No clinically significant slit lamp findings (i.e. corneal oedema, significant staining, central scarring, infiltrates, active neovascularisation)
 - No other active ocular disease (including pterygia)

Exclusion Criteria:

- i. Previous anterior ocular surgery
- ii. Any active corneal infection, injury or inflammation
- iii. Large pinguecula likely to affect soft lens fit
- iv. Systemic or ocular disease or medication which might interfere with CL wear
- v. Pregnancy or breastfeeding
- vi. Participation in any concurrent trial

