3 STUDY DESIGN & RATIONALE

This will be a one-day, double-masked, randomised, repeated measures study. Each subject will wear the three lens types (Acuvue® OASYS® with HydraClear Plus™ in two base curves and 1-Day Oasys with HydraLuxe™ in one base curve). A total of six lenses will therefore be worn by each subject (3 per eye).

An attempt will be made to include subjects who have large corneas or have previously demonstrated loose / tight fitting contact lenses since eyes with larger corneas tend to be less successful in contact lens fitting.

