5 STUDY POPULATION

5.1 Number of Subjects

Approx. 50 subjects (40-60 subjects) who fulfil the inclusion criteria will be fitted with study contact lenses.

In order to fully explore the hypothesis an attempt will be made to include subjects who have an HVID of >11.75mm, Corneal Diameter of >13.75mm, or who have exhibited 'loose' or 'tight' lens fittings in previous studies.

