11.1 Sample Size Rationale

A sample size of 60 subjects showing a 90% success rate would give an 80% confidence interval of $\pm 5.0\%$. This would statistically differentiate success rates of 85% and 95%.

A sample size of 60 is sufficient to detect a mean difference of 5 (0-100) in tightness, or 0.2 mm in corneal overlap assuming the standard deviation of the mean differences in Table 2 below and assuming $\alpha=0.05$ with a power of 95%.

Table 2: Sample Size Justification:

	Sample Size	
	Tightness (0-100)	Corneal overlap (mm)
Mean of paired difference	5	0.2
SD of paired difference	10	0.4
Minimum sample size per group	42	42

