11.2 Level of Statistical Significance

The overall type I error rate will be preserved at 5%. To preserve type I error control, the study hypotheses will be evaluated using a sequential gate-keeping strategy. All tests will be two-sided. The three co-primary hypotheses will be simultaneously evaluated using $\alpha=0.05$, all of which must be met in order to satisfy the primary objective of this study.

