11.3 Analysis Population

The primary hypotheses will be analysed on all randomized subjects who have successfully completed the study without a protocol deviation that is deemed to impact the assessment of the primary hypotheses (i.e. the per-protocol population).

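### The minimum of 42 in the sample size table gives 88.6% power, not the stated 95%; on the table's own inputs 95% needs 54 subjects, above the central target of about 50

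*Protocol*

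**What the plan says.** Section 11.1 argues from 60 subjects. It says that number can detect a mean difference of 5 points in tightness (0-100 scale) or 0.2 mm in corneal overlap, at α=0.05 and "with a power of 95" per cent, using the standard deviations in its Table 2 (Sample Size Justification; the visit schedule in 8.2.8 is also numbered Table 2). That table gives SDs of the paired difference of 10 points and 0.4 mm. Its last row, "Minimum sample size per group", reads 42 for both variables. The table prints no power of its own.

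Section 11.2 adds "All tests will be two-sided". Section 5.1 plans "Approx. 50 subjects (40-60 subjects) who fulfil the inclusion criteria will be fitted with study contact lenses", and the synopsis says "Approximately 40-60 subjects". Section 11.3 restricts the primary analysis: "The primary hypotheses will be analysed on all randomized subjects who have successfully completed the study without a protocol deviation" that is judged to affect the primary hypotheses.

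**The concern.** The only power stated in 11.1 is 95%, and the sentence that states it sends the reader to the table for its assumptions. The natural reading is that 42 is the smallest number giving 95% power. If that is wrong, the table makes almost the whole 40-60 range look adequate at 95% when its lower half is not.

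Tightness and corneal overlap are the subject of hypothesis iii. Under 11.2 all three co-primary hypotheses must be met, so this component bears on the success of the whole study. The number that counts is per-protocol completers, which can be lower than the number enrolled.

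The row label is also loose. Every subject wears all three lens types, so there are no groups, only pairs within subject.

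**Working it through.** **Inputs, all from the protocol**

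- Mean paired difference and SD (11.1, Table 2): 5 and 10 points; 0.2 and 0.4 mm. Standardised effect d = 5/10 = 0.2/0.4 = 0.5 for both, so one calculation serves both columns.
- α = 0.05 and power 95% (11.1); two-sided (11.2).
- Unit: one value per subject. Section 11.1 counts subjects and makes no adjustment for eyes.

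**Trying to reproduce 42**

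Normal approximation: n = ((z₁₋α/₂ + z_power)/d)².

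- 95% power: ((1.960 + 1.645)/0.5)² = 51.98, so 52.
- 90% power: ((1.960 + 1.282)/0.5)² = 42.03.

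The printed 42 therefore matches a two-sided normal calculation at 90% power, not 95%. That this is where it came from is an inference. One-sided testing at 95% does not give 42 either: it needs 44 (normal) or 45 (t).

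**Power by number of subjects**

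Paired t: noncentral t with n − 1 degrees of freedom and noncentrality 0.5√n. Normal: Φ(0.5√n − 1.960). At n = 42, 0.5√42 = 3.240, and Φ(3.240 − 1.960) = Φ(1.280) = 90.0%.

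| Subjects | Paired t | Normal |
|---|---|---|
| 40 | 86.9% | 88.5% |
| 42 | 88.6% | 90.0% |
| 50 | 93.4% | 94.2% |
| 53 | 94.65% | 95.4% |
| 54 | 95.0% | 95.7% |
| 60 | 96.8% | 97.2% |

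The first n to reach 95% by the t-test is 54.

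**What 42 can detect**

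By the t-test, 95% power at n = 42 requires d = 0.570: 0.570 × 10 = 5.7 points, or 0.570 × 0.4 = 0.228 mm. At n = 40 it requires d = 0.585, which is about 5.8 points or 0.234 mm.

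**Sensitivity to the unit**

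Assume instead that the SDs are per eye and both eyes are averaged, with between-eye correlation r. Then d = 0.5/√((1 + r)/2).

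| r (assumed) | d | Power at 42 | Power at 50 |
|---|---|---|---|
| 0.5 | 0.577 | 95.5% | 97.9% |
| 0.8 | 0.527 | 91.5% | 95.5% |
| 1 | 0.500 | 88.6% | 93.4% |

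On this assumption 42 reaches 95% only if r is at most about 0.54.

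**The case against.** The arithmetic is not in dispute. The case on the other side concerns scope and weight.

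- **The 95% is attached to 60, where it is correct, and the table names no power.** The 42 could be an unlabelled 90% calculation, which would make this a labelling mismatch. That may well be the origin, but no 90% appears anywhere in 11.1, so a reader cannot know it. The row is still wrong for the only power stated.
- **Nothing says the table justifies 40-60.** This stands in part. Both paragraphs of 11.1 argue from 60, and the first offers a separate precision argument for success rates. The link from 42 to the lower end of the range is an inference. Section 5.1 and the synopsis make no power claim and are not themselves in error.
- **The effect is small.** At 42 the detectable difference moves from 5 to 5.7 points and from 0.20 to 0.23 mm, while overlap is recorded to 0.1 mm. That limits the weight of the finding but does not make the figure right.
- **Both eyes are used.** The design section says "A total of six lenses will therefore be worn by each subject (3 per eye"), and the protocol elsewhere speaks of proportions of eyes. With a between-eye correlation near 0.5, 42 would do. The protocol gives no such correlation, and 11.1 counts subjects.
- **Hypothesis iii is equivalence to model values, while 54 comes from a test of a difference.** This stands as a caution. For illustration, assume a margin of 0.5 SD, a true difference of zero and a 95% interval required to lie within the margin. The normal approximation 2Φ(0.5√n − 1.96) − 1 then gives about 91% at 54 and 94% at 60. The protocol states no margin, so 54 corrects the calculation that 11.1 describes and does not certify power for the equivalence claim.

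**Conclusion.** The concern holds. For the paired-difference calculation in 11.1, with d = 0.5, two-sided α = 0.05 and one value per subject, the minimum for 95% power is 54 by paired t-test (52 by normal approximation), not 42. The printed number is 12 subjects short of the t-test figure and gives 88.6% power. The statement about 60 subjects is correct.

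The 95% claim fails from 40 to 53 analysed subjects, which includes the central target of about 50. The shortfall there is moderate: 8.1 percentage points at 40 (95.0 − 86.9) and 1.6 at 50 (95.0 − 93.4). It should be corrected, but it does not undermine the design. The conclusion rests on the subject being the unit; it would change only if the SDs were per eye with a between-eye correlation of at most about 0.54.

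**What to change.** - **Table 2 in 11.1:** print 54 for 95% power and name the method and unit (paired t-test, two-sided α = 0.05, one value per subject). Alternatively keep 42 and state its power as 88.6% (t) or 90.0% (normal). Label the row as subjects (paired).
- **Text of 11.1:** give power over the planned range (87% at 40, 93% at 50, 97% at 60) and tie the 95% claim to 54 or more per-protocol completers. Say that this is power to detect a difference.
- **Section 5.1 and synopsis:** either keep 40-60 and refer to that power statement, or, if 95% is really wanted, set the target at 54 or more completers.
- **If both eyes are meant to count:** state the between-eye correlation assumed and recompute.

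The cost is a text change in 11.1 and its table, with a matching line in 5.1 and the synopsis. Nothing requires more than the planned 60. If 54 completers are required, 60 leaves room for 60 − 54 = 6 losses from the per-protocol set, and only a few more subjects than the central 50 are needed.

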11.2 Level of Statistical Significance

The overall type I error rate will be preserved at 5%. To preserve type I error control, the study hypotheses will be evaluated using a sequential gate-keeping strategy. All tests will be two-sided. The three co-primary hypotheses will be simultaneously evaluated using $\alpha=0.05$, all of which must be met in order to satisfy the primary objective of this study.

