1 INTRODUCTION

Since ocular topographies vary within the population,¹ it is important that contact lens designs are selected that comfortably and successfully fit a wide range of eyes. Multiple designs generally give a wider coverage of the population than single designs. Because soft contact lenses are generally not available in a wide range of parameters, it is difficult to evaluate the effectiveness of design combinations. However, senofilcon A lenses have recently become available in multiple diameters, which offers the opportunity to explore the utility of various design combinations.

Computer modelling provides useful insights into the relationship between lens design and fit and allows an estimation of the fitting success rate for a given lens design on a given population.^{2,3} Recent calculations suggest that a combination of multiple diameter designs is likely to be more successful than multiple base curves of identical lens diameter.⁴

The main purpose of this study is to evaluate the fitting success of various combinations of senofilcon A lens designs. A secondary purpose will be to evaluate the validity of the Young soft contact lens fit model.²

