2.1 Hypotheses

The following hypotheses will be tested:

- i. The fitting success rate for a combination of two senofilcon A designs is greater than for a single design when fitted to a population skewed to larger corneas.
- ii. The fitting success rates for senofilcon A designs are equivalent to those predicted by the Young model.
- iii. The fitting characteristics (tightness, corneal overlap) for senofilcon A designs are equivalent to those predicted by the Young model.

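### Section 11.2 sets two incompatible testing rules, leaving the status of the lens-combination result undetermined when the fit-model hypotheses fail

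*Protocol*

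**What the plan says.** Protocol section 11.2 makes four statements that bear on this point:

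- "The overall type I error rate will be preserved at 5" per cent.
- To secure this, "the study hypotheses will be evaluated using a sequential gate-keeping strategy".
- "All tests will be two-sided".
- "The three co-primary hypotheses will be simultaneously evaluated using" alpha of 0.05, "all of which must be met in order to satisfy the primary objective of this study".

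Section 2.1 lists exactly three hypotheses. Hypothesis i is a superiority statement: "The fitting success rate for a combination of two senofilcon A designs is greater than for a single design", in a population skewed to larger corneas. Hypothesis ii is an equivalence statement: "The fitting success rates for senofilcon A designs are equivalent to those predicted by the Young model". Hypothesis iii makes the same kind of statement for tightness and corneal overlap.

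Section 1 (Introduction) ranks these questions. It gives lens-design combinations as the main purpose and then adds: "A secondary purpose will be to evaluate the validity" of the Young fit model. Hypothesis i belongs to the main purpose, and ii and iii belong to the secondary one.

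**The concern.** A gate-keeping sequence and a simultaneous all-must-be-met rule treat partial success differently. In a sequence, a claim made at an early step stands even if a later step fails. Under the co-primary rule there is no order and no credit for meeting only some of the hypotheses. Section 11.2 prescribes both and gives neither an order nor a gate.

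The study's main question is at stake. Suppose two designs clearly fit more eyes than one, but the Young model's predictions are not confirmed. By the Introduction's ranking, the main question has been answered. By the last sentence of section 11.2, the primary objective has not been satisfied. The protocol does not say whether the lens-combination result may then be reported as a confirmed finding. A choice made after the data are seen would be open to challenge.

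**Working it through.** **Step 1. Reproduce the stated 5%.** Each rule is taken alone, with each test at 0.05.

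- *Fixed sequence.* A false claim requires rejecting the first true null hypothesis in the order. The probability of that is at most 0.05, so the familywise error is at most 5%.
- *All three must be met.* A false overall success requires rejecting at least one true null hypothesis at 0.05. The probability is again at most 5%.

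The stated figure is therefore reproduced under either rule. An error of 1 − 0.95³ = 0.143 would arise only if any one of three independent tests could be claimed by itself with no order. Neither rule allows that.

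**Step 2. Look for a reading that reconciles the sentences.** The three co-primaries might form a first gate with lower-tier hypotheses behind it. But section 2.1 has only three hypotheses and section 11.2 calls all three co-primary. Nothing lies behind the gate, so the gate-keeping sentence would have no content. This reading would also leave the main question dependent on the model results.

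**Step 3. Compare the rules by outcome.** The first position of hypothesis i is inferred from the Introduction and from the listing order in sections 2 and 2.1. Section 11.2 does not state it.

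| Outcome | Sequence starting with i | All must be met |
|---|---|---|
| i, ii and iii all met | all claims stand | primary objective satisfied |
| i met, ii or iii not met | claim on i stands | primary objective not satisfied |
| i not met | no claim | primary objective not satisfied |

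The conflict is confined to the middle row. If the sequence started with ii or iii instead, failure there would mean that i was never formally tested, so the missing order matters as well.

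**Step 4. How often the middle row occurs.** The protocol gives no power for any of the three hypotheses. Section 11.1 quotes 95% power, but for detecting mean differences in tightness and overlap, not for showing equivalence. The powers below are therefore assumptions, with equal power p for each hypothesis. Under independence:

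P(i met, ii or iii not met) = p − p³

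- p = 0.80: 0.80 − 0.512 = 0.288
- p = 0.90: 0.90 − 0.729 = 0.171
- p = 0.95: 0.95 − 0.857 = 0.093

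The tests share the same eyes, so positive correlation is plausible. Simulation with normally distributed test statistics gives:

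| Power each | Correlation 0 | Correlation 0.5 | Correlation 0.8 |
|---|---|---|---|
| 80% | 29% | 19% | 11% |
| 90% | 17% | 12% | 7% |
| 95% | 9% | 7% | 4% |

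**Step 5. Can each step be decided?** Hypotheses ii and iii claim equivalence. Sections 11.5.2 and 11.5.3 rely on 95% confidence intervals and give no margin, so the protocol does not define when ii or iii is met. Either rule in section 11.2 needs that definition.

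**The case against.** The strongest reply is that only one sentence in section 11.2 defines success for the primary objective, and it requires all three hypotheses. Run as a fixed sequence at 0.05, passing all three is the same event as passing all three simultaneously. This stands. A reader might infer that the same data could make the primary objective both a success and a failure, but the text does not support that. What remains open is whether hypothesis i may be claimed by itself when ii or iii fails.

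A reader might also infer that the 5% claim is false because each hypothesis covers several lenses or lens pairs. Three two-sided contrasts at 0.05 give 12.5% (correlation 0.5) to 14.3% (independent) for at least one rejection. The documents do not support this inference either. It needs a rule that any one contrast is enough, which the protocol never states, and ii and iii read naturally as requiring every design to agree. For the directional hypothesis i it also counts rejections in the wrong direction. Counting only false claims of a greater success rate gives 1 − 0.975³ = 7.3% if independent, or 6.3% at correlation 0.5.

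Nor should 51% or 73% (0.80³ or 0.90³) be read as this trial's joint power. They rest on assumed powers and independence. With 95% each, joint power is 86% if independent and 88% at correlation 0.5.

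Finally, requiring all three is a legitimate, stricter choice, and sections 2 and 2.1 do not rank the hypotheses. That is fair. If it is the intention, however, the gate-keeping sentence and the Introduction's ranking need to change. An SAP, not available here, could add detail, but whichever rule it chose would depart from a sentence in the protocol.

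**Conclusion.** The contradiction is real but narrow. Section 11.2 prescribes two testing rules that cannot both be followed, gives no order for the first, and leaves it nothing to gate. Its all-must-be-met rule also departs from the Introduction's ranking of purposes. As a result, the status of the main lens-combination result is undetermined when i is met and ii or iii is not.

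Alpha inflation across the three hypotheses is not the fault, since each rule alone keeps it at 5% or less. The conflicting pattern would occur in about 29% to 9% of trials for assumed powers of 80% to 95% each under independence, and in 19% to 4% with correlations of 0.5 to 0.8. These figures illustrate scale and are not estimates for this trial. They also assume that the sequence starts with hypothesis i. The contradiction itself depends on none of these figures.

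**What to change.** Keep one rule. The option in line with the Introduction is:

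- Test hypothesis i first at two-sided 0.05. Only if it is met, test ii, and only if that is met, test iii, each at 0.05 in this fixed order.
- Delete the sentence that evaluates the three as simultaneous co-primaries and requires all of them.
- Name the pair-versus-single contrasts that make up hypothesis i, and say whether all or any one must succeed. Apply Holm if any one is enough.
- Give equivalence margins for ii and iii, so that each step has a defined result.

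If the sponsor does intend all three as co-primary, delete the gate-keeping sentence instead, bring the Introduction into line, and state the joint power. Margins for ii and iii are needed here too.

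Either option is a change of wording in the protocol, carried through to any SAP, and needs no new measurements. The cost of the fixed sequence is that model validation becomes formally secondary, as the Introduction already describes it. The cost of the co-primary option is that the main question cannot be concluded by itself.

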11.3 Analysis Population

The primary hypotheses will be analysed on all randomized subjects who have successfully completed the study without a protocol deviation that is deemed to impact the assessment of the primary hypotheses (i.e. the per-protocol population).

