3.1 Randomisation

Subjects will wear each of the three lens types bilaterally in random succession. A random number generator (Microsoft Excel) will determine the randomisation of lenses to subjects, which is then incorporated into the Randomisation Log.

The randomised assignment of subjects will be performed at the first assessment prior to the first randomised lens fitting. The following must be ensured prior to randomisation:

- Informed consent has been obtained
- Subjects meet all inclusion / exclusion criteria
- Subject history and baseline information have been collected

Subjects who are discontinued may be replaced in order to achieve the targeted minimum number of cohort subjects, but the ID number will not be reused.

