5.6 Subject Replacement

Subject IDs will not be reused should a subject drop-out or be discontinued from the study. If subjects are discontinued or drop out of the study, new subjects may be enrolled to ensure adequate subject numbers complete the study.

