8.2.3 Baseline Assessment

The following baseline measurements and assessments will be recorded:

- i. Subject demographics, age, sex, medications, allergies
- ii. Monocular spherocylindrical refraction (sphere, cylinder and axis)
- iii. Monocular and binocular high contrast (HC) distance visual acuity (logMAR) with best spherocyl spectacle refraction [D]
- iv. Baseline Biometry measurements
 - Corneal topography: Sim-K-readings and corneal shape factor (Medmont)
 - HVID* (photo slit lamp)
 - Palpebral Aperture (mm)
 - Corneal sagittal height, corneal diameter (CD) (Visante OCT).
- * From photographs
- v. Slit lamp biomicroscopy
 - Limbal Hyperaemia (0-4)
 - Bulbar Hyperaemia (0-4)
 - Palpebral Hyperaemia (0-4) and roughness (0-4)
 - Corneal staining (0-4)
 - Conjunctival fluorescein staining (0-4)
 - Other findings (0-4).

See Appendix 6 for Grading Scales and measurement instructions.

Rinse away fluorescein with non-preserved saline (e.g. Sauflon saline) and allow at least 2 minutes for tear film to reform.

- vi. Complete the eligibility checklist.

The subject's eligibility will be assessed for the study ensuring that the subject meets all of the inclusion/exclusion criteria, and full ocular health must be established. If the subject is eligible, then they can be fitted with the study lenses, if not eligible, then the reason should be noted on the Enrolment Log and the Exit CRF should be completed before the subject exits from the study.

Enter the subject number on to the next line of the Randomisation Log to identify the first pair of study lenses.

8.2.4 1st Pair Study Lens Assessment

- i. Complete the Product Dispensing Foil Log.
- ii. Record the parameters of the lenses on the 1st Pair Study Lens Assessment CRF (lens code, lens power). Lenses powers should be chosen as close as possible to the subject's spherical refraction based upon habitual contact lens information and refraction.

- iii. Confirm lens is undamaged (Y/N). If yes, replace and complete Product Dispensing Foil Log.
- iv. Insert 1st pair of study contact lenses.
- v. Confirm subjects comfort and vision is satisfactory (Y/N). If no, then remove, replace and complete Product Dispensing Foil Log, and then repeat section v.
- vi. If yes, allow approximately 30-45 minutes settling period.
- vii. After settling, record the following on the 1st Pair Study Lens Assessment CRF:
 - Lens Fit
 - Horizontal* & vertical* centration / overlap (mm)
 - Post-blink movement in primary gaze (mm)*

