Biometry		
Corneal Topography Sim-K	Assessed using Medmont Corneal Topographer.	To nearest 0.01 mm
Corneal Topography Corneal Shape Factor (P-value)	Assessed using Medmont Corneal Topographer.	To nearest 0.01 mm
Iris Diameter	Assessed using photographs from photo slit lamp (10x or 30x magnification), at primary gaze and using the eyepiece graticule.	To nearest 0.1 mm
Palpebral Aperture	Assessed using slit lamp in 10x or 30x magnification, at primary gaze and using the eyepiece graticule.	To nearest 0.1 mm
Corneal Sagittal Height	Assessed using Visante OCT.	To nearest 0.01 mm
Corneal Diameter	Assessed using Visante OCT.	To nearest 0.01 mm
Lens Fit - assessed using photo / video slit lamp (10x or 30x magnification)		
Horizontal and Vertical Centration / overlap	Assessed using photographs / video, primary gaze and eyepiece graticule. Lens centration will be recorded by degree and direction in the primary position.	To nearest 0.1mm For Superior or Nasal record +ve value For Inferior or Temporal record -ve value
Post-Blink Movement in Primary Gaze	Assessed using photographs / video, primary gaze and using the eyepiece graticule immediately after the blink - lower lid to be depressed only if necessary for observation.	To nearest 0.1mm
Version Lag	Assessed on D / L gaze.	To nearest 0.1mm

VARIABLE	ASSESSMENT METHOD	GRADING/MEASUREMENT SYSTEM
Edge Tightness	Assessed using primary gaze and eyepiece graticule.	Grade 0-4 where: 0 Gross edge stand-off/fluting 1 Loose, occasional edge lifting 2 Optimum 3 Tight, mild vessel compression 4 Conjunctival indentation and/or compression against immobile lens
Tightness / Push-up	Assessed by digital push-up test (gentle push of the lens upward using the lower lid) with eye in primary gaze position and observing ease of push-up and speed of return to original position.	Grade 0%-100% continuous scale where: 100% No movement 50% Optimum 0% Falls from cornea without lid support
Diameter Acceptance	Assessed using primary gaze and the eyepiece graticule.	To nearest 0.1mm
Overall Fit Acceptance	Assessed by the Investigator based on lens fit alone (i.e. not comfort or vision).	Grade 0-5 & add reason if Grade 2 or less: 0 Should not be worn 1 Should not be dispensed although no immediate danger 2 Borderline but unacceptable 3 Min. acceptable, early review 4 Not perfect but OK to dispense 5 Perfect
Comfort		

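### Restricting every primary hypothesis to per-protocol completers discards fit-related discontinuations, with no rule for counting them

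*Protocol*

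**What the plan says.** Protocol 11.3 names one population for the primary hypotheses: the randomised subjects "who have successfully completed the study without a protocol deviation" judged to affect the assessment of those hypotheses. Section 11.2 treats all three hypotheses as co-primary and requires all of them to be met. The restriction therefore covers the superiority claim (i) as well as the two equivalence claims (ii and iii).

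Replacement is allowed in two places. Section 3.1 states "Subjects who are discontinued may be replaced in order to achieve the targeted minimum number of cohort subjects", and section 5.6 states that "new subjects may be enrolled to ensure adequate subject numbers complete the study". Under 9.5, completing means reaching the assessment of the third pair.

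In 8.2.4, each lens must pass a comfort and vision check before it settles and is graded. On a failed check the instruction is "If no, then remove, replace and complete Product Dispensing Foil Log, and then repeat section v". Only then comes "If yes, allow approximately 30-45 minutes settling period", followed by the fit grading. Sections 8.2.5 and 8.2.6 repeat this for the second and third pairs. No recorded outcome is given for a lens that never passes.

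Appendix 5 describes overall fit acceptance as "Assessed by the Investigator based on lens fit alone (i.e. not comfort or vision". It is graded 0-5, and Grade 2 is labelled "2 Borderline but unacceptable".

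**The concern.** The endpoint is whether a lens fits, so stopping because a lens cannot be worn carries information about the endpoint. Section 11.3 removes that subject entirely, including any acceptable or unacceptable grades already recorded on other lenses, and the place may go to someone who tolerates all three pairs. The mixed models in 11.5 can use incomplete subjects, so the loss is avoidable.

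The check in 8.2.4 adds a second route. Acceptance is defined on fit alone, yet comfort and vision decide whether a fit grade is made at all. If a lens never passes and the subject stops, there is no grade for that lens and no subject in the analysis.

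Recruitment makes fit-related stopping more plausible than in an ordinary sample, because sections 3 and 5.1 seek large corneas and eyes with previous loose or tight fits. Hypothesis ii is the most exposed: section 11.5.2 sets the absolute success rate of each lens against a theoretical value, so an error in the absolute rate enters that comparison directly.

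**Working it through.** **The plan's own figure.** Section 11.1 gives 60 subjects, a 90% success rate and an 80% interval of ±5.0%. The Wald half-width is 1.2816 × √(0.9 × 0.1 / 60) = 0.0496, or 4.96 points, so the figure reproduces. Section 11.5.2 uses 95% intervals. On the same inputs the half-width is 1.960 × √(0.9 × 0.1 / 60) = 0.0759, or 7.6 points.

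**Error in the absolute rate.** Take 60 completers (after any replacement) with 54 acceptable, one outcome per subject and lens. Let k be the number of randomised subjects left out and q the share of them whose fit would be unacceptable. Both are assumptions, since the protocol gives no drop-out rate.

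- Rate with the excluded subjects counted: (54 + k(1 − q)) / (60 + k)
- Overstatement by completers only: 0.90 − that rate = k(q − 0.10) / (60 + k)

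| k | q | Rate with excluded counted | Overstatement (points) |
|---|---|---|---|
| 1 | 1 | 54/61 = 88.5% | 1.5 |
| 2 | 1 | 54/62 = 87.1% | 2.9 |
| 3 | 1 | 54/63 = 85.7% | 4.3 |
| 6 | 1 | 54/66 = 81.8% | 8.2 |
| 3 | 0.5 | 55.5/63 = 88.1% | 1.9 |
| 6 | 0.5 | 57/66 = 86.4% | 3.6 |
| 3 or 6 | 0.10 | 90.0% | 0 |

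Three excluded fit failures would use most of the 80% half-width, or a little over half of the 95% one. The formula turns negative if excluded subjects fit better than completers.

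**Direction for hypothesis i.** Assume that a pair of designs succeeds when at least one of its two lenses is acceptable, and compare it with a single design belonging to that pair. Among 60 completers let the single design succeed in 54 and the pair in S, with S from 54 to 60. Add one excluded subject.

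- *The subject fails the single design but had an acceptable grade on the other lens.* The gap with the subject kept is (S + 1 − 54)/61; with the subject dropped it is (S − 54)/60. Kept minus dropped is (114 − S)/3660, which is 1.6 points at S = 54 and 1.5 at S = 60. Completers-only understates the gain from two designs.
- *The subject fails both.* The gap is (S − 54)/61 kept and (S − 54)/60 dropped. Dropped minus kept is (S − 54)/3660, at most 6/3660 = 0.2 points. Completers-only slightly overstates the gain.

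The sign therefore depends on who stops and on which lens.

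**The case against.** A reader might infer that the plan strips poor fits out of the denominator. It does not. Grades 0 to 2 describe unacceptable fits, section 8.2.4 asks for a reason at those grades, and a subject so graded who reaches the third assessment stays in as a failure. Bias needs a further event, a fit-related withdrawal within one visit of about 3.5 hours, and this may be rare.

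A reader might also infer that swapping a lens removes an eye. It does not: the replacement is graded under the same randomised code. Nor is there literally no way out of the repeated check, because 8.2.1 and 8.3 allow discontinuation at any time with a recorded reason. What is missing is how that case counts towards the success rate.

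It is tempting to say that completers-only flatters the superiority claim. The arithmetic above does not support that as a general statement, since the loss can just as well hide a gain from two designs.

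A per-protocol set is a usual choice for equivalence hypotheses. Section 11.3 speaks only of the primary hypotheses, and 11.5.4 leaves room for further analyses. An analysis plan that is not shown may add supportive sets.

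These points make the bias conditional and narrow the claim. They do not remove it: the protocol itself fixes completers as the primary population for a superiority hypothesis, and it gives no rule for counting a lens-related discontinuation.

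**Conclusion.** The concern holds in conditional form. Section 11.3, read with the replacement rules, discards outcome-related discontinuations and the valid grades that go with them. If those discontinuations are fit-related, absolute success rates are biased upward, chiefly for hypothesis ii. For hypothesis i the comparison may be distorted in either direction.

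Under the assumptions of 60 completers at 90%, one outcome per subject and lens, and exclusions that are all fit failures, the overstatement is 1.5 points for one exclusion and 4.3 for three. It is zero if excluded subjects fail at the completers' rate, or if nobody is excluded. The documents do not support a claim that the bias will occur, or any particular size. Counting eyes, as 11.5.2 does, would change the figures but not the reasoning.

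**What to change.** - **Hypothesis i.** Define the primary set as all randomised subjects with at least one study lens inserted, analysed by eye and lens. Keep the partial data of subjects who stop, including those later replaced.
- **Ungraded eye-lenses.** Count one left ungraded for a fit-related reason as unacceptable. Treat one left ungraded for comfort or vision alone as missing, with a sensitivity analysis that scores it as a failure. Scoring it as a failure in the main analysis would conflict with the fit-only definition in Appendix 5 and could push actual rates down against the theoretical ones, which rest on edge strain and corneal overlap only.
- **Hypotheses ii and iii.** Report both this set and the per-protocol set, and require the conclusions to agree.
- **Reconcile the passages.** State how the comfort and vision check in 8.2.4 fits with the fit-alone definition in Appendix 5, and what is recorded when a lens never passes.

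The cost is wording, one extra analysis run and possibly slightly lower success rates. Section 8.3 already has the primary reason for discontinuation on the exit form, with room for comments, and the foil log covers replaced lenses.
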